Statistical Methodology	General linear mixed models will be used to test the primary and secondary hypotheses; of interest will be the main effect of treatment, treatment x time, and treatment x time x treatment phase. Analyses will include data from all randomized subjects who received at least one dose of study medication and participated in at least one post-baseline efficacy assessment.		

1 Introduction

This document is a protocol for a human research study. This study is to be conducted according to US and international standards of Good Clinical Practice (FDA Title 21 part 312 and International Conference on Harmonization guidelines), applicable government regulations, and University of North Carolina research policies and procedures.

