If the dose is reduced during the course of the study, the participant will continue the lowered dose for the remainder of the study. If adverse events do not improve within 14 days of lowering the dose, the investigational product may be permanently discontinued at the discretion of the treating study physician, participant, and participant's guardian. If a participant exhibits extreme exacerbation of behavioral symptoms (such as self-injurious behavior or aggression) that do not improve substantially following a dose reduction and are determined "probably" or "definitely" related to taking the investigational product, the investigational product may be permanently discontinued sooner than 14 days post-reduction, and the DSMB will be notified. As individuals with ASD often have cyclical changes in behavior independent of medication effects, the study staff will rely on caregivers' experience with the participant to determine if any observed behavior changes are within the expected range for that individual. If the investigational product is stopped permanently, the participant and his caregiver will be asked to complete the remainder of the study visits, return any unused study drug, and repeat safety lab studies.

2 Study Objectives

Primary Objective:

The primary objective of this clinical trial is to determine if Avmacol[®] is superior to placebo for improving social communication impairment in adolescent and young adult men with moderate to severe autism spectrum disorder (ASD), as measured by change in Social Responsiveness Scale-2 (SRS-2) [100] total scores.

Secondary Objectives:

Secondary objectives include: (1) assessing the safety and tolerability of Avmacol[®] in subjects with ASD; and (2) characterizing the effects of Avmacol[®] on behavioral challenges commonly associated with ASD, including hyperactivity, irritability, repetitive behavior, and inappropriate speech.

Exploratory Objectives:

In a subset of 30 participants, exploratory objectives include: (1) Assessment of gut micobiota diversity and relative abundance of microbial species from fecal samples collected before and after 12 weeks of treatment with sulforaphane or placebo. (2) Explore the relationship between changes in microbiota composition and behavioral outcomes in young men treated with sulforaphane or placebo.

3 Study Design

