Vital signs and reports of adverse events will be monitored at each study visit (Baseline, Week 4, Week 8, Week 12, Week 16) for tolerability and safety monitoring. A phone call with the subject's caregiver at Week 2 of the treatment phase will also be used to monitor for early adverse events. Physical exam and phlebotomy for routine laboratories (Complete Blood Count (CBC); Comprehensive Metabolic Panel (CMP); Liver Function Tests (LFTs), and Thyroid Stimulating Hormone (TSH)) will be conducted at Baseline and Week 12 for the purposes of safety monitoring. Fecal samples will be collected at home in the 48 hr prior to Baseline and Week 12 visits for microbiota analyses.

Schematic Diagram of Study Events:

¹ Behavioral outcome measures (SRS-2, ABC, CGI, RBSR)

²Adverse Events Review

³ Blood chemistries (Comprehensive Metabolic Panel, Liver Function Tests, Thyroid Stimulating Hormone)

Primary Study Endpoints

The primary study endpoint will be percent change in mean SRS-2 total scores from Baseline to Week 12, the end of the active treatment phase.

Secondary Study Endpoints

- Percent change in mean SRS-2 total scores from Week 12 (the end of the active treatment phase) to Week 16 (the end of the discontinuation phase)
- Percent change in mean SRS-2 subscale scores (Social Awareness, Social Cognition, Social Communication, Social Motivation, and Restricted Interests/ Repetitive Behaviors) from Baseline to Week 12 and from Week 12 (the end of the active treatment phase) to Week 16 (the end of the discontinuation phase)
- Change in mean CGI-Severity score from Baseline to Week 12 and from Week 12 (the end of the active treatment phase) to Week 16 (the end of the discontinuation phase)
- Proportion of participants with CGI-Improvement (CGI-I) scores of 1 (very much improved) or 2 (much improved) in each treatment arm at Weeks 12 and Week 16
- Percent change in mean RBSR total scores from Baseline to Week 12 and from Week 12 (the end of the active treatment phase) to Week 16 (the end of the discontinuation phase).
- Percent change in mean ABC subscale scores (Social Withdrawal, Hyperactivity, Inappropriate Speech, Stereotypy, and Irritability) from Baseline to Week 12 and from Week 12 (the end of the active treatment phase) to Week 16 (the end of the discontinuation phase)

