7.1 Sample Size Determination

We calculated power for comparing groups on change in SRS-2 total score (the primary outcome measure), using a standard approach for linear mixed models (Littell RC, Milliken GA, Stroup WW, Wolfinger RD, Schabenberger O. *SAS for mixed models [electronic resource]*. Cary, N.C.: SAS Institute, Inc.; 2006). We assumed that the mean differences observed in the trial by Singh et al. represented the true values (i.e., we assumed mean differences of 7, 20, 18.4, and 0.4 at weeks 4, 8, 12 and 16, respectively), and we assumed a constant standard deviation of 20, consistent with that observed by Singh et al. Furthermore, we assume within-participants across time correlation of 0.5 (a conservative value) and we assume no more than 15% loss distributed over the 16 weeks of follow-up. Under these assumptions, randomizing 27 participants to each group will provide at least 80% power for an overall test comparing groups across all time points using a two-sided 4 degree of freedom test at the 0.05 significance level.

For the exploratory microbiota analysis, we aim to include a subset of 30 subjects in the sample. In a recent randomized cross-over trial of the effects of broccoli consumption on microbiota composition in 18 healthy adults [Kaczmarek 2017*], participants consuming broccoli exhibited an increase in the ratio of Baceteroidetes to Firmicutes by 37% from baseline to end, compared to a 5% reduction during the control period (p=0.02). With 15 participants per group, we will have >80% power to detect a similar change in the ratio of Bacteroidetes to Firmicutes.

* Kaczmarek JL, et al. Broccoli consumption impacts the human gastrointestinal microbiota. The FASEB Journal, 2017. 31(1 suppl): p.965.

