7.2 Statistical Methods

General linear mixed models (GLMM) will be used to test the primary and secondary hypotheses in longitudinal analyses:

Primary Hypotheses

Compared to control participants, treated participants will show larger changes over time on SRS-2 total scores from Baseline to Week 12, and differences will not be maintained after treatment discontinuation at Week 12 through the end of the follow-up period at Week 16.

GLMM analyses will describe individual patterns of change over time on the SRS-2 Total score. Individual intercepts and slopes will be estimated as random-effects variables, and will be allowed to correlate. The SRS-2 scores from Baseline, Week 4, 8, 12, and 16 will be modeled as a function of treatment, time, time x treatment and will include covariates of age-stratum and the SRS-2 total score from screening. In addition to time, we will add a time-varying variable representing treatment phase (0=treatment, 1=follow-up period) and we cross this variable with treatment, time, and treatment x time. Time will be centered at Week 12. Of interest will be the main effect of treatment (i.e., treatment impact at end of active treatment), treatment x time (i.e., treatment impact on change over time during the active treatment phase), and treatment x time x treatment phase (i.e., treatment differences in change over time during follow-up period). We will use an unstructured covariance matrix. We will first test for any differences between groups across all four groups using a 4 degree of freedom linear contrast of the model parameters. If this overall test is significant at the 5% level, we will then test for differences separately at each time point. We will also report estimated mean differences along with 95% confidence intervals.

Secondary Hypotheses

Compared to control participants, treated participates will show larger changes over time on CGI Severity and RBSR scores from Baseline to Week 12 and will show reduction in those gains after discontinuation through the end of the follow-up period at Week 16.

Compared to control participants, treated participates will show larger changes over time on subscales when treatment impacts were observed on the total scores on the SRS-2, CGI Severity, and RBSR from Baseline to Week 12 and will show reduction in those gains after discontinuation through the end of the follow-up period at Week 16.

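### The primary endpoint is a percent change with no estimator or test, no Week 12 test is named as deciding the primary objective, and the section 7.2 model cannot be run together with its own 4-df gate

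*Combined protocol and SAP*

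**What the plan says.** - **Endpoint.** Section 3.1, Primary Study Endpoints: "The primary study endpoint will be percent change in mean SRS-2 total scores from Baseline to Week 12". The primary objective in section 2 has no percent scale and no visit: "as measured by change in Social Responsiveness Scale-2 (SRS-2) [100] total scores". Section 7.1 also refers to change in the total score.
- **Powered test.** Section 7.1 powers "an overall test comparing groups across all time points using a two-sided 4 degree of freedom test", assuming differences at Weeks 4, 8, 12 and 16.
- **Model.** Section 7.2 models the scores at Baseline and Weeks 4, 8, 12 and 16, with time centred at Week 12. "Individual intercepts and slopes will be estimated as random-effects variables, and will be allowed to correlate". It adds "a time-varying variable representing treatment phase (0=treatment, 1=follow-up period) and we cross this variable with treatment, time, and treatment x time". It explains the treatment main effect as the effect at the close of active treatment.
- **Decision step.** Section 7.2 begins with a 4-df contrast, described as spanning four groups although the trial has two arms. Then: "If this overall test is significant at the 5% level, we will then test for differences separately at each time point".
- **Synopsis.** The Study Summary does not mention the overall test: "of interest will be the main effect of treatment, treatment x time, and treatment x time x treatment phase". Section 7.2 lists the same three effects.
- **Phases.** Section 6.7 places Week 12 at the end of the active phase. Section 6.8 places Week 16 four weeks after treatment stops.

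**The concern.** The endpoint, the powered test and the listed effects are different quantities, and nothing ranks them. If the gate fails, section 7.2 permits no visit test, so that case is settled. If the gate is significant and Week 12 is not, the plan does not say whether the primary objective is met. Percent change, the overall test, the Week 12 visit test and the model's treatment coefficient could each later be presented as the primary result.

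The model adds a second problem. Section 7.2 asks for a 4-df contrast, individual slopes, and a phase variable that changes at only one visit. An analyst would have to drop or recode something to fit it, and the choice changes what the Week 12 coefficient estimates.

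**Working it through.** **Inputs (section 7.1).** Differences d = (7, 20, 18.4, 0.4) at Weeks 4, 8, 12, 16; SD 20; correlation r = 0.5; 27 per arm; up to 15% loss over 16 weeks. Effective numbers per arm: 27 (no loss); 27 × (1 − 0.15 × 12/16) ≈ 24 (even loss, as at Week 12); 27 × 0.85 ≈ 23 (all loss early).

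**1. The plan's own figure.** With equal correlation 0.5, the noncentrality is (n/2) × [Σd² − 0.2(Σd)²]/200. Here Σd² = 787.72 and Σd = 45.8, so the bracket is 787.72 − 419.53 = 368.19. At n = 27 this gives 13.5 × 1.841 = 24.85. Power from the noncentral F (4, 2n − 5 df) is 98/96/95% at 27/24/23 per arm. The claim of at least 80% holds.

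**2. Percent scale.** Section 7.2 gives an analysis of percent change for the exploratory Bacteroidetes to Firmicutes ratio, but none for SRS-2. The documents give no Baseline mean and no SD of percent change, so power on that scale cannot be computed. For an assumed Baseline mean of 80 to 140, 18.4 points is 23% to 13%.

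**3. The undefined outcome.** Gate by Hotelling F, Week 12 by two-sample t, simulated from the inputs above without the screening covariate:

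| True differences | Gate significant (27/24/23) | Gate significant, Week 12 not |
|---|---|---|
| As planned | 98/96/95% | 8/10/11% |
| All four halved | 44/39/38% | 17/16/15% |
| Week 12 alone halved (9.2) | 92/87/86% | 54/54/54% |
| Week 12 alone zero | 95/91/90% | 90/86/85% |

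The last three rows are illustrative. The last two apply only if Week 12 falls while Week 8 stays at 20. In the last row the gated Week 12 test rejects in 5% of trials, as it should.

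**4. The model, coded three ways.** Time in weeks from Week 12 is −12, −8, −4, 0, 4.

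- *Linear time, phase = 1 at Week 16 only (follows section 6.7).* Time × phase = 4 × phase. The treatment columns (1, time, phase, time × phase) have rank 3, so no 4-df contrast exists. Dropping one aliased term makes all three listed effects estimable. The treatment effect is then the end of a line through Weeks 0 to 12, with weights 1/4 + 6(t + 6)/80 = −0.2, 0.1, 0.4, 0.7. Its expectation is 0.1 × 7 + 0.4 × 20 + 0.7 × 18.4 = 21.6 against 18.4, and 0.7 + 8 = 8.7 if the true Week 12 difference is 0. These weights hold under equal correlation, or for a random intercept and slope fit with independent residuals. With an unstructured visit covariance and AR(1) correlation of 0.5 to 0.7 (illustrative), the expectations are 20.2 to 19.5, and 5.1 to 3.4.
- *Categorical visits.* The 4-df test and the Week 12 difference both exist. Phase is simply the Week 16 indicator: rank is 5 before and after adding the phase terms. No separate treatment × time × phase effect remains.
- *Linear time, Week 12 coded as follow-up.* Rank is 4, so 4 df exist. But this contradicts section 6.7, and the treatment effect becomes an extrapolation from Weeks 0 to 8: mean 9 at Week 4, slope 20/8 = 2.5 per week, so 9 + 2.5 × 8 = 29.0 against 18.4. It no longer matches section 7.2's own explanation of that effect.

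**5. Week 12 as the deciding test.** SD of change = 20 × √(2(1 − r)), which is 20 at r = 0.5. Power by noncentral t for 18.4 points at 27/24/23 per arm is 91/88/86%. At r = 0.3 it is 80/75/73%; at r = 0.7, 99/98/98%.

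**The case against.** Modelling raw scores is a normal way to analyse change in points, and section 7.2 compares arms at Week 12 twice: through the centred treatment effect and through the gated visit test. A reader might infer that the endpoint is tied to no test at all. That goes too far: only the percent scale lacks a test, and what is missing at Week 12 is the designation.

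A reader might also infer that the model cannot produce its listed effects. It can, under linear time, once one aliased term is dropped. The change in slope is then −28/4 = −7.0 points per week (SE 1.5 at 27 per arm). What fails there is the 4-df contrast and the reading of the coefficient as the Week 12 difference. The 4 df and the visit-by-visit tests lean towards categorical visits, where those two problems disappear. But section 7.2 also calls for individual slopes, centred time and a phase crossing, which then have no role.

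The 54% and 85 to 90% figures need Week 12 alone to fall, so they do not describe a uniformly weaker treatment. Adding the screening covariate at the same correlation lowers the planned-profile figure to about 3 to 5%. These points limit the size. They do not supply the missing decision rule.

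Testing Week 16 is deliberate, since the primary hypothesis expects the difference to fade after stopping. That supports keeping the overall test, but it does not make that test evidence for a Week 12 endpoint.

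**Conclusion.** The point holds as a specification error with three parts: an endpoint on a scale that has no estimator or test; no rule for a significant gate with a non-significant Week 12 result; and a model that cannot be run as written with its 4-df contrast. The undefined outcome has a probability of about 8 to 11% under the section 7.1 assumptions without the screening covariate, and 15 to 17% if all differences are halved. Under the linear coding that fits section 6.7 and equal correlation, the Week 12 coefficient is off by 3.2 points (21.6 − 18.4) on the planned profile and by 8.7 points if the true Week 12 difference is zero. Linear time is implied by the centring and slopes, not stated.

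A reader might take this as a finding of low power or inflated type I error. The documents support neither: the stated power is exceeded, and with categorical visits the gated Week 12 test keeps its 5% level at a cost of only 1 to 2 points of power.

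**What to change.** In an amendment dated before any comparison by arm:

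1. Make change in SRS-2 total in points the primary endpoint, and report percent change descriptively.
2. Replace linear time, phase and random slopes with categorical visit, visit-by-treatment terms and an unstructured covariance across visits. Keep the age stratum.
3. State that the between-group difference in change from Baseline to Week 12, two-sided 5%, decides the primary objective.
4. Fix how Baseline enters. Closest to section 7.2: keep Baseline as an outcome visit, keep the screening score as covariate, and use the Week 12 minus Baseline contrast.
5. Correct the reference to four groups so that it means the four post-baseline visits. Keep the overall test and the Week 12 to Week 16 contrast as secondary.
6. Restate power for the Week 12 contrast, and align the Study Summary and sections 2, 3.1, 7.1 and 7.2.

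Sample size is unchanged. Section 8.1 shows that enrolment has begun, so the date of the amendment matters. The cost is power: 91/88/86% for the Week 12 contrast against 98/96/95% for the overall test if the assumed profile is exactly right, and 80/75/73% if r is 0.3, below the value that section 7.1 calls conservative.

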3.1 General Design

We propose to conduct a Phase II, randomized, double-blind, placebo-controlled trial of Avmacol®, a rich source of sulforaphane, for the treatment of social impairment in individuals with ASD. Fifty-four male subjects with autism spectrum disorder (ASD) between ages 13 and 30 years old will be randomized in a 1:1 ratio, stratified by age category (13-18 and 19-30 years old), to receive either Avmacol® or identical placebo tablets. Participation will be limited to males to closely approximate the sample used in the SF for ASD clinical trial by Singh et al. [48] and to account for possible mechanistic differences in ASD between males and females (ASD is 4 times more common in males). Stratification by age will account for possible age-based differences in response to treatment (adolescence vs. adulthood) and allow for secondary analysis by age group (adolescent vs. adult).

The length of study participation from baseline to study termination for each individual subject is 16 weeks, including a 12-week active treatment phase (Avmacol® or placebo), followed by a 4-week blinded discontinuation phase. Participants will be monitored with clinic visits at regular intervals (baseline and weeks 4, 8, 12, and 16) for improvement in a well-characterized, caregiver-rated measure of social impairment (Social Responsiveness Scale-2 (SRS-2) [100], the primary outcome) as well as secondary measures of (1) repetitive behaviors associated with ASD (Repetitive Behavior Scale- Revised; RBSR) [102]; (2) challenging behaviors commonly associated with developmental disabilities (Aberrant Behavior Checklist; ABC) [103]; (3) clinician-rated functional severity (Clinical Global Impression Scale- Severity; CGI-S) [104]; and clinician-rated functional improvement (Clinical Global Impression Scale- Improvement; CGI-I) [104].

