5.3 Method for Assigning Subjects to Treatment Groups

Enrolled participants will be stratified for age (13-18 and 19-30 years) to account for possible effects of age on treatment response. The goal is to recruit twenty-seven 13-18 year-olds and twenty-seven 19-30 year-olds to allow for separate analysis of adolescents and adults (exploratory). Individuals will be randomly assigned to treatment group within age strata by generating random numbers for each group for each entry (i.e., 1-27 for younger group and 1-27

for older group). The larger half of the random numbers within each group will be assigned to receive the treatment and the smaller half to the placebo condition. These two lists – listed in their original order (1-27 for younger and 1-27 for older) will be provided to UNC Investigational Drug Services (IDS) pharmacists. They will consult the list and provide the appropriate medication to each individual depending on the order in which they present to the pharmacy within their age group. Study personnel will remain blinded to treatment condition for the duration of the study.

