Similar GLMM analyses will be conducted to examine the longitudinal assessments of CGI Severity and RBSR and of subscales if the total scores show treatment impacts.

Exploratory Hypotheses

We hypothesize that treatment with sulforaphane will result in greater diversity of gut microbial species and a higher ratio of Bacteroidetes to Firmicutes spp. compared to placebo, and that these alterations in gut microbiota will be positively associated with behavioral improvements in the sulforaphane treatment group.

We will utilize Genotek's validated wet-lab and metagenomic data analytic pipeline for the batched sample processing and data analysis. Microbial DNA will be extracted and amplified using PCR, and 16S rRNA gene sequencing will be performed using the Illumina MiSeq platform. A curated taxonomic database will be used to assign a taxonomic classification to the sequencing reads. The mean (%) relative abundance of microbial phyla and genera will be calculated for the sulforaphane and placebo groups pre- and posttreatment. The percent change in Bacteroidetes to Firmicutes (B:F) ratio from baseline to endpoint will be compared between treatment groups using Analysis of Covariance (ANCOVA), with baseline B:F ratio included as a covariate.

Microbiota diversity and relative abundance will be assessed using conventional within sample ("alpha diversity") and between-sample ("beta diversity") metrics. Three metrics will be used to assess change in alpha diversity over time: the absolute number of operational taxonomic units (OTUs), Chao1 estimator, and Shannon index. We will use ANCOVA to test for significant differences in alpha diversity from baseline to endpoint within each treatment group. Beta diversity will be assessed with 3 metrics: Bray-Curtis dissimilarity, Weighted Unifrac distance, and Unweighted Unifrac distance. These indices will be used to determine the variance in an individual over time and the mean dissimilarity between individuals in each group. Weighted Unifrac distance distance will be used for Principal Coordinates Analysis (PCoA). We will create a PCoA plot to visually identify whether samples from each treatment group cluster together at different time points (before and after treatment). This can help determine whether any changes identified during beta diversity analysis are directed changes or random noise.

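### The B:F comparison between arms leaves out the age stratum used in randomisation, which gives up some precision if age predicts the change in B:F

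*Combined protocol and SAP*

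**What the plan says.** Section 3.1 has participants "randomized in a 1:1 ratio, stratified by age category (13-18 and 19-30 years old"). Section 5.3 gives the reason: they are "stratified for age (13-18 and 19-30 years) to account for possible effects of age on treatment response". Allocation runs from two separate lists of 27, one per age group.

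In section 7.2 the SRS-2 model "will include covariates of age-stratum and the SRS-2 total score from screening". The secondary outcomes get similar mixed models. The microbiota comparison is a separate analysis under the exploratory hypotheses: percent change in B:F is "compared between treatment groups using Analysis of Covariance (ANCOVA), with baseline B:F ratio included as a covariate". Nothing in section 7 carries the age stratum into this ANCOVA.

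On size, section 7.1 says "we aim to include a subset of 30 subjects in the sample" and "With 15 participants per group, we will have >80% power to detect a similar change in the ratio of Bacteroidetes to Firmicutes". Section 2 lists the microbiota aims as exploratory. The documents do not say how the 30 are chosen from the 54, or whether the subset is balanced by age within arm.

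**The concern.** When allocation is balanced within a factor, the treatment estimate hardly varies with that factor. A model that omits the factor still counts the variance it explains as error. The standard error is then larger than it needs to be, the interval is too wide and the test is somewhat conservative. If the analysed subset is not balanced by age, the estimate also varies with the chance age difference between arms, and adjustment removes that variation.

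The plan treats age as important enough to stratify on and to include in its primary model. It drops age from the one microbiota comparison for which it states a power. With 15 per arm, precision is scarce, and the stratum is known for every participant. What is at stake is interval width and power in an exploratory comparison.

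**Working it through.** **The plan's own figure.** Section 7.1 states more than 80% power with 15 per group but gives no SD, alpha or baseline correlation for B:F, so the figure cannot be strictly reproduced. An SD can be backed out from the cited cross-over study of 18 adults, where the ratio rose "by 37% from baseline to end, compared to a 5% reduction during the control period (p=0.02"). This takes the p-value as a paired t-test and assumes two-sided 0.05 for the present trial.

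- Difference: 37 − (−5) = 42 percentage points.
- t for two-sided p = 0.02 on 17 df is 2.567, so SE = 42 / 2.567 = 16.4.
- SD of the within-person difference = 16.4 × √18 ≈ 69.4.
- Per-period SD = 69.4 / √(2(1 − ρ)), which is 49.1, 56.7 or 69.4 for ρ = 0, 0.25 or 0.5.
- Power of a t-test with 15 per arm: 62, 50 or 36%.

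The SD that would give 80% is 39.6. Whether the stated power is right is a separate question from the covariate. It matters here only because the SD, and so the effect in SD units, has to be assumed.

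**Cost of the extra covariate.** With 30 participants, the planned ANCOVA leaves 30 − 3 = 27 df, and adding the stratum leaves 26. The critical values are t(27) = 2.0518 and t(26) = 2.0555, a ratio of 1.0018.

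**Gain.** Let R² be the share of residual variance, given baseline B:F, that the stratum explains. With balance within strata, the interval width with adjustment divided by the width without is about √(1 − R²) × 1.0018. The break-even is R² = 1 − (2.0518 / 2.0555)² ≈ 0.004, or 0.4%. That counts the degree of freedom only; 8:7 and 7:8 splits raise it slightly. For a random 30 of the 54, the simulated ratio is 1.011 at R² = 0, 1.001 at 0.02 and 0.985 at 0.05, so break-even is at about 2%.

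**Size.** Take age as 5, 10 or 20% of total variance and baseline B:F as 10%, so that R² = share / 0.90:

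- 5%: R² = 0.056; √0.944 × 1.0018 = 0.974
- 10%: R² = 0.111; √0.889 × 1.0018 = 0.945
- 20%: R² = 0.222; √0.778 × 1.0018 = 0.883

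Simulation of both ANCOVAs with a true effect of 1 SD agrees (power is without → with the stratum):

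| Age share of total variance | Random 30 of 54: narrowing | Random 30 of 54: power | Balanced strata: narrowing | Balanced strata: power |
|---|---|---|---|---|
| 5% | 2% | about 76 → 79% | 3% | 76 → 80% |
| 10% | 5% | about 76 → 81% | 6% | 75 → 82% |
| 20% | 11% | about 76 → 86% | 12% | 75 → 87% |

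If age explains nothing, the interval widens by about 0.5% (balanced) to 1.2% (random 30), and power falls by nothing to about 1 to 2 points.

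**Error rate.** For R² of 5, 10 and 20%, the planned interval covers 95.4, 95.3 and 96.1% with a random 30, and 95.5, 95.8 and 96.7% with balanced strata. The corresponding type I error is 4.6, 4.7 and 3.9%, and 4.5, 4.2 and 3.3%. None exceeds 5%.

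**At the implied SD.** With SD 49.1 the effect is 42 / 49.1 = 0.86 SD. Balanced strata with R² of 5, 10 or 20% then move power from 61.8% to 63.9, 66.2 or 71.3%.

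**The case against.** The strongest reply is that nothing here is invalid. The endpoint is exploratory, the estimate is unbiased over randomisation, and any error in the test is on the conservative side. All of that stands, and it is why the point is minor.

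The second reply is that the driving input is missing. No figure in the documents says that being 13-18 rather than 19-30 predicts the change in B:F. The outcome is change from the participant's own baseline, with baseline adjusted as well, so age differences in the level of the ratio are largely handled already. The reason given for stratifying is a possible effect of age on treatment response. That is effect modification, which an additive age term does not address. This stands as a limit on size: the gain is conditional, and zero is within the range. It does not remove the case for the covariate, because the possible loss from including it is small and bounded.

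The third reply is that balance by age is designed for the 54, not for the 30. This also stands, so the random-subset column is the safer guide.

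A reader might infer four stronger things that the documents do not support:

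- **That precision is lost whenever age matters at all.** Below the break-even share, adjusting widens the interval.
- **That the test runs clearly below its nominal level.** With a random 30 and R² of 10% or less, the shortfall is barely visible.
- **That the covariate decides whether the power claim of more than 80% is met.** At the SD of 49.1 implied by the cited p-value, power stays below 80% in the balanced-strata calculation even when the stratum explains 20% of residual variance.
- **That every microbiota model needs the stratum for the same reason.** The alpha-diversity ANCOVA is described within each treatment group, and the microbiota-behaviour models test association. Neither is a randomised comparison between arms, so the argument from stratified allocation does not reach them.

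**Conclusion.** The point holds as a minor matter of efficiency. The B:F ANCOVA omits a factor that the trial randomises by and adjusts for in its primary model. Validity is not at issue. Precision is lost only if the age stratum explains more than roughly 0.4 to 2% of the residual variance in B:F change, depending on how well the 30 are balanced.

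Over an assumed 5 to 20% of total variance, the loss is about 2 to 11% of interval width for a random 30 and 3 to 12% with balanced strata. These sizes rest on a baseline share of 10%, an effect of 1 SD and complete data on 30 participants, none of which the documents establish. If age is irrelevant, leaving it out is very slightly better.

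**What to change.** In section 7.2, specify the B:F ANCOVA as treatment + baseline B:F + age stratum (13-18, 19-30). Fix this before unblinding, and in any case before treatment codes are joined to the sequencing results. Limit the change to the B:F comparison between arms.

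The cost is one line of wording and one degree of freedom out of 27. No new data are needed. The downside, if age turns out not to matter, is an interval about 0.5 to 1.2% wider and up to about 1 to 2 points of power.
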